8.3 Interim Analysis

No interim analyses are planned. The study data will be analyzed when the sample size requirements are met.

8.4 Primary Endpoint Analysis

The primary analysis will be completed on the Per Protocol population and will consist of all evaluable subjects enrolled in the study who have documented recurrent flat or sessile colorectal lesions up to 6 cm in diameter and/or length and are treated with the Interscope device without adjunctive modality. The analysis will be conducted on the percent of lesions with persistent disease. The primary endpoint is:

Technical Success, defined as the ability of the EndoRotor device to resect recurrent flat or sessile colorectal lesions without concomitant use of other resection modalities for mucosectomy and no definitely and probably device-related serious adverse events (SAEs) throughout the 90-day follow-up period.

This analysis population will be used to describe the primary effectiveness and the secondary endpoints. A confidence interval for the successful removal of all lesions will be calculated by Clopper-Pearson exact methods⁶ if all subjects are treated for one lesion. In the event that one or more subjects are treated for multiple lesions, then a generalized estimating equation with a logistic link function will be used to estimate the 95% confidence interval of the success rate.

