	the Interscope, Inc. Quality Management System. Interscope, Inc. is ISO 13485 certified (FM 61310).		
Study Design:	Post-market, prospective, non-randomized, multi-center study for the treatment of subjects with the need for resection of recurrent flat or sessile colorectal lesions where EndoRotor is the primary resection modality of persistent adenoma with a scarred base.		
Enrollment:	Total enrollment is at least 60 evaluable subjects at up to 15 clinical sites		
	I .		

	in the United States and Europe.				
Subject Population:	Adult subjects aged ≥18 to ≤85 years who have one or more recurrent				
	flat or sessile rectal/colon mucosal polyps measuring up to 6 cm in				
	diameter and/or length.				
Estimated Study	First subject enrolled: June 2019				
Duration:	Last subject enrolled: December 2019				
	Study completion (final 90-day visit, closeout visit): June 2020				
Primary Endpoints:	Primary Effectiveness Endpoint (Performance):				
	Technical Success, defined as the ability of the EndoRotor device to				
	resect recurrent flat or sessile colorectal lesions without concomitant use				
	of other resection modalities for mucosectomy and no definitely or				
	probably device-related serious adverse events (SAEs) throughout the				
	90-day follow-up period.				
	Primary Safety Endpoint:				
	Assessment of Serious Adverse Events (incidence, relationship to device				
	and severity) at index procedure and at 90 days, post-procedure.				
Secondary Endpoints:	2 2 2				
v I	and/or photographs and in addition to diagnostic assessment of				
	specimen graded by the independent pathologist.				
	2. Presence of colon stenosis based on endoscopy film and/or				
	photographs.				
	3. Rate of persistence of disease at the location of resection at 90 days.				
	4. Histologic assessment of the diagnostic value of the collected				
	specimens.				
Primary Analysis:	The Per Protocol (PP) analysis population will be the primary				
	effectiveness analysis population.				
Inclusion Criteria:	1. Subjects aged ≥18 to ≤85 years.				
	2. At least one recurrent flat or sessile colorectal lesion measuring up to				
	6 cm in diameter and/or length. 3. Presence of recurrent flat or sessile lesion where the EndoRotor®				
	may be used to resect recurrent neoplasia.				
	4. Favorable anatomy that allows the investigator to access the lesion.				
	5. Subject is able and willing to comply with site standard medical				
	follow-up, including the 90-day follow-up visit.				

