4.2 Secondary Endpoints

The following is a list of other secondary endpoints to be explored:

- 1. Completeness, in percentage, of resection based on endoscopy film and/or photographs in addition to diagnostic assessment of specimen by the independent pathologist.
- 2. Presence of colon stenosis based on endoscopy film and/or photographs.
- 3. Rate of persistence of disease at the location of resection at 90 days.
- 4. Histologic assessment of the diagnostic value of the collected specimens.

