4.3 Inclusion Criteria

Subjects are required to meet **ALL** the following inclusion criteria in order to be included in this clinical study:

- 1. Subjects aged \geq 18 to \leq 85 years.
- 2. At least one recurrent flat or sessile colorectal lesion up to 6 cm in diameter and/or length.
- 3. Presence of lesion where the EndoRotor® may be used to resect recurrent neoplasia.
- 4. Favorable anatomy that allows the investigator to access the lesion.
- 5. Subject is able and willing to comply with site standard medical follow-up, including a 90-day follow-up visit.
- 6. Subject has been informed of the nature of the study, agrees to participate and has signed the consent form

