8.2 Analysis Populations

Two analysis populations are defined for this protocol, Intent to Treat and Per Protocol.

Intent to Treat Population: All subjects in whom the EndoRotor was used for any resection of a lesion. This includes those subjects that were either treated with the EndoRotor alone or with another adjunctive modality.

Per Protocol (PP): Subset of the Intent to Treat population including those subjects who had complete lesion resection with the EndoRotor alone without any adjunctive modality resection, did not have inclusion/exclusion protocol deviations and completed the 90 day follow up visit. The effectiveness analyses will be conducted on the per protocol population.

Safety Population: Defined as all subjects who were treated with the device.

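### Section 8.4 does not tie its stated analysis to Technical Success, and its Per Protocol population removes the resection failures which that endpoint should count

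*Combined protocol and SAP*

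**What the plan says.** **Endpoint.** Section 4.1, the Protocol Summary and Section 8.4 all give Technical Success as the primary effectiveness endpoint. It has two parts: the device resects the recurrent lesions without another resection modality, and there is no definite or probable device-related SAE through 90 days.

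**Analysed variable.** Just before restating that endpoint, Section 8.4 says "The analysis will be conducted on the percent of lesions with persistent disease". Section 4.2 lists this outcome as a secondary endpoint: "Rate of persistence of disease at the location of resection at 90 days". Section 8.4 goes on: "A confidence interval for the successful removal of all lesions will be calculated by Clopper-Pearson exact methods" if every subject has one lesion. If any subject has several, "a generalized estimating equation with a logistic link function will be used to estimate the 95% confidence interval of the success rate".

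**Population.** The Protocol Summary (Primary Analysis) says "The Per Protocol (PP) analysis population will be the primary" effectiveness population, and Sections 8.2 and 8.4 agree. Section 8.2 restricts that set to "those subjects who had complete lesion resection with the EndoRotor alone without any adjunctive modality resection", with no eligibility deviation and a completed 90-day visit. Intent to Treat is "All subjects in whom the EndoRotor was used for any resection of a lesion". It keeps converted subjects, but no effectiveness analysis is assigned to it.

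**Failures foreseen.** Section 5.7 lets the investigator convert to another modality when EndoRotor cannot complete the resection. Section 5.3 describes attempts aborted before any tissue is resected; these subjects are followed to discharge for safety and may then exit.

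**The concern.** Two things do not fit together.

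First, an analyst following Section 8.4 could report a 90-day persistence rate, a removal rate or Technical Success as the primary result. The text does not choose among them.

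Second, the resection half of Technical Success is used as an entry rule for the population in which Technical Success is estimated. A subject who needed another modality is a failure by the endpoint definition, but is excluded before the rate is calculated.

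The plan has no hypothesis test and no success threshold, so this estimate and its interval are the effectiveness result. The Protocol Summary says that the study will confirm safety and effectiveness. A rate from which the device's resection failures have been removed cannot carry that conclusion.

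**Working it through.** **1. The plan's own figure.** Section 8.8 takes n = 60 and a success rate of 0.85, and states a 95% exact interval of 0.782 to 0.967 with half width 0.0972. The Clopper-Pearson limits for x successes in n are the 0.025 quantile of Beta(x, n − x + 1) and the 0.975 quantile of Beta(x + 1, n − x). With x = 0.85 × 60 = 51, the interval is 0.734 to 0.929, half width 0.0974. The half width reproduces to within 0.0002. The stated limits do not; they match 45/50 (0.782 to 0.967). That mismatch is a separate matter, and nothing below depends on it.

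**2. Endpoint against population.**

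| Event | Technical Success (4.1) | Intent to Treat (8.2) | Per Protocol (8.2) |
|---|---|---|---|
| Converted to another modality (5.7) | Failure | Included | Excluded |
| Attempt aborted, no tissue resected (5.3) | Not resected | Apparently excluded | Excluded |
| EndoRotor alone, device-related SAE | Failure | Included | Included if 90-day visit done |
| EndoRotor alone, no SAE, 90-day visit missed | Not fully observed | Included; missing endpoint dropped (8.9) | Excluded |

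Within Per Protocol, the first part of the endpoint is met by everyone. Only the SAE part can produce a failure.

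**3. Size.** The documents give no conversion rate, so the counts are assumptions. Take 60 treated subjects, full follow-up, no eligibility deviations, one result per subject, c conversions and s device-related SAEs among the others. Then

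- Intent to Treat = (60 − c − s)/60
- Per Protocol = (60 − c − s)/(60 − c)

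With s = 0, Per Protocol equals 1 for every c, and its lower limit is 0.025^(1/(60 − c)).

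| c | Intent to Treat (95% CI) | Per Protocol (lower limit) |
|---|---|---|
| 3 | 57/60 = 0.950 (0.861 to 0.990) | 57/57 = 1.000 (0.937) |
| 6 | 54/60 = 0.900 (0.795 to 0.962) | 54/54 = 1.000 (0.934) |
| 9 | 51/60 = 0.850 (0.734 to 0.929) | 51/51 = 1.000 (0.930) |
| 12 | 48/60 = 0.800 (0.677 to 0.892) | 48/48 = 1.000 (0.926) |

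With c = 9 and s = 1, the figures are 50/60 = 0.833 and 50/51 = 0.980. With c = 9, s = 0 and 2 aborted attempts (assumed) added as failures, the rate is 51/62 = 0.823 (0.705 to 0.908).

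**4. Missing 90-day visits.** Section 5.4 caps expected loss at 10%, which is 6 of 60. Take c = 9, s = 0 and the worst case, in which all 6 losses fall among the 51 successes. Counting them as failures gives 45/60 = 0.750 (0.621 to 0.853). Dropping them, as in Section 8.9, gives 45/54 = 0.833 (0.707 to 0.921). Per Protocol gives 45/45 = 1.000. If the loss is roughly proportional, about 5 of the 51 are lost and the first two figures become 46/60 = 0.767 and 46/55 = 0.836.

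**5. The planned 0.85.** If this is Technical Success in a Per Protocol set of 60, the failures number 0.15 × 60 = 9, and all must be definite or probable device-related SAEs. If it refers to freedom from persistence, it implies 15% persistence, which lies within the 1.4 to 24% recurrence range in Section 1.3.2 and needs no SAE.

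**The case against.** The study is observational and its analysis is mainly descriptive. The success rate in the last sentence of Section 8.4 follows the endpoint definition, and together with the rule for binary endpoints in Section 8.0 it can reasonably be read as Technical Success. Converted subjects remain in the Safety population, and the index-procedure form (Section 5.7.1) records for every subject whether the device achieved the resection. Per Protocol still informs on SAEs and on persistence.

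All of that is correct, and it limits the point: the failures are recorded. But no section assigns them to an effectiveness analysis, and reading the success rate as Technical Success leaves the denominator unchanged.

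A reader might infer more than the documents support:

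- *That the planned 0.85 proves the sample size assumed 9 SAEs.* This follows only on one reading. On the persistence reading it fails, so 0.85 is supporting evidence at most.
- *That persistence is plainly the wrong variable.* Sections 4.1 and 8.4 and the Protocol Summary favour Technical Success, but the sponsor may have meant persistence to measure the ability to resect. The documents show a conflict and do not settle it.
- *That the generalized estimating equation is an error.* It is a legitimate method for several lesions per subject. It has no finite estimate only if there are no failures and at least one subject has several lesions.
- *That the second treatment visit undermines the endpoint.* Section 5.7 permits it, and neither the endpoint nor Per Protocol requires a single session. Saying how it counts is a clarification.

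**Conclusion.** The point stands and should be fixed before analysis. Section 8.4 names one primary endpoint and describes the analysis of other quantities. Its population is selected on the resection result, so the resection part of Technical Success is 100% by construction. No section puts the conversions back.

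For a removal rate or Technical Success, the estimate is biased upward whenever a conversion occurs. With no SAE, the gap from Intent to Treat is c/60: 0.05 to 0.20 for 3 to 12 conversions. At 9 conversions the whole Intent to Treat interval (upper limit 0.929) lies below the Per Protocol lower limit (0.930). The sizes rest on assumed conversion counts and full follow-up; the direction rests on the definitions alone. For a persistence rate, the documents do not show which way excluding conversions would move the result.

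**What to change.** 1. State in Section 8.4 that the analysed primary variable is Technical Success as defined in Section 4.1, and report 90-day persistence as the secondary endpoint it is listed as. If the sponsor intended persistence as the primary measure, the Protocol Summary and Sections 4.1, 4.2 and 8.4 must be reconciled to say so.
2. Make the primary effectiveness population all subjects in whom EndoRotor resection was attempted, that is, Intent to Treat plus attempts aborted without tissue resection. Count use of another resection modality or an aborted attempt as failure. An aborted attempt is classified at the procedure, so exit at discharge leaves no gap. Keep Per Protocol as supportive.
3. Do not drop subjects resected by EndoRotor alone who miss the 90-day visit (Section 8.9) without a sensitivity analysis that counts them as failures.
4. Amend the Protocol Summary and Sections 4.1, 8.2, 8.4 and 8.9 together, and state which population the 60 evaluable subjects in Sections 3.1.2, 5.4 and 8.8 counts.

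The cost is a wording amendment, with IRB notification if it is judged substantial (Section 9.3). The resection result and SAEs are already collected. If evaluable has so far meant Per Protocol, the change could also alter when enrolment stops, and that should be settled in the same amendment. The reported success rate will probably be lower.

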8.6 Secondary Endpoint Analysis

The secondary endpoints will be characterized using descriptive statistics.

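### All secondary endpoints are described only in the Per Protocol set, which selects on device-alone success, eligibility and 90-day return; each endpoint needs its own set and denominator

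*Combined protocol and SAP*

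**What the plan says.** Section 8.4 opens with "The primary analysis will be completed on the Per Protocol population" and later adds "This analysis population will be used to describe the primary effectiveness and the secondary endpoints", so the set meant is Per Protocol. Section 8.2 defines it by three conditions: "Subset of the Intent to Treat population including those subjects who had complete lesion resection with the EndoRotor alone without any adjunctive modality resection", and further that subjects "did not have inclusion/exclusion protocol deviations and completed the 90 day follow up visit".

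Section 8.6 says only this: "The secondary endpoints will be characterized using descriptive statistics". It names no population. Section 8.2 also defines Intent to Treat and Safety sets, but no secondary endpoint is assigned to either.

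Section 4.2 lists four secondary endpoints: percent completeness of resection, stenosis ("Presence of colon stenosis based on endoscopy film and/or photographs"), persistence at the resection site at 90 days, and specimen value ("Histologic assessment of the diagnostic value of the collected specimens").

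The data are collected more widely than they are to be summarised:

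- Section 5.7.1 collects the index-procedure items, including whether the specimens could be interpreted, on all subjects.
- Section 5.8 records stenosis and persistence at the 90-day endoscopy without limiting this to device-alone subjects.
- Section 5.7 permits conversion to another modality, and Section 8.2 keeps converted subjects in Intent to Treat.
- Section 5.3 keeps treated subjects later found ineligible in follow-up.

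**The concern.** One set, conditioned on procedural success, is applied to four endpoints of different kinds.

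- **Stenosis** is a harm of resection. A converted or ineligible subject whose 90-day endoscopy shows stenosis does not count towards the endpoint.
- **Specimen value** depends on tissue retrieved at the index procedure. Whether the subject "completed the 90 day follow up visit", or later needed another tool, has no bearing on whether that tissue could be read, yet either excludes the result.
- **Completeness** is summarised among subjects already classed as completely resected, so it can hardly inform.
- **Persistence** leaves out the lesions that could not be cleared with the device alone.

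If stenosis is more frequent, or specimens harder to read, in the excluded subjects, the planned summaries cannot show it. Section 1 presents tissue for histology as an advantage of the device over ablation, so selection in the specimen endpoint bears on a claim the sponsor makes.

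**Working it through.** **1. The plan's own figure.** Section 8.8 gives, for n = 60 and success 0.85, an exact 95% interval of 0.782 to 0.967 and a half-width of 0.0972. Clopper-Pearson for 51/60 gives 0.734 to 0.929, half-width 0.0974. The half-width agrees to within 0.0002; the interval is not reproduced. That is a separate matter. Only the 60 and the 0.85 are used below.

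**2. Inputs.**

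- N = 60 treated. This is an assumption: Sections 3.1.2 and 5.4 speak of 60 evaluable subjects.
- s = 0.85 from Section 8.8, taken as the share fully resected with the device alone. This is also an assumption, because Technical Success further requires no definitely or probably device-related SAE.
- d = 0.10 from Section 5.4, the anticipated maximum loss, assumed independent of success.
- No eligibility deviations; any would add to the omissions.

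**3. Central case.**

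- Per Protocol = N × s × (1 − d) = 60 × 0.85 × 0.90 = 45.9.
- Omitted in all = 60 − 45.9 = 14.1, made up of 60 × 0.15 = 9.0 not resected by the device alone and 60 × 0.85 × 0.10 = 5.1 resected by it but lost. All 14.1 can have a specimen result.
- Returned at 90 days = 60 × 0.90 = 54.
- Returned but omitted = 60 × 0.15 × 0.90 = 8.1. These are the avoidable stenosis and persistence omissions.

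**4. Range, per 60 treated.**

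| s | d | Per Protocol | Omitted in all | Returned but omitted |
|---|---|---|---|---|
| 0.95 | 0 | 57.0 | 3.0 | 3.0 |
| 0.95 | 0.10 | 51.3 | 8.7 | 2.7 |
| 0.85 | 0 | 51.0 | 9.0 | 9.0 |
| 0.85 | 0.10 | 45.9 | 14.1 | 8.1 |
| 0.80 | 0 | 48.0 | 12.0 | 12.0 |
| 0.80 | 0.10 | 43.2 | 16.8 | 10.8 |

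**5. If the 60 evaluable subjects must all be Per Protocol.** Treated = 60 / (0.85 × 0.90) = 78.4, so 79, and 79 − 60 = 19 are omitted.

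**6. Precision.** With zero stenoses the two-sided 95% upper limit is 1 − 0.025^(1/n): 7.7% for n = 46 and 6.6% for n = 54. The difference is small, and the Per Protocol limit is the less favourable one.

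**7. Selection.** The documents give no stenosis or readability rates by group, so these are assumed.

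- Stenosis at 2% in device-alone subjects and 5%, 10% or 20% in the others gives 0.85 × 2% + 0.15 × (5%, 10%, 20%) = 2.5%, 3.2% or 4.7% overall, while Per Protocol still shows 2%.
- Specimens readable in 90% of device-alone subjects and 50% to 70% of the others give 84% to 87% overall, against 90% in Per Protocol.

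**The case against.** The strongest defence is attribution. After conversion, stenosis or persistence may be due to the other modality, so a device-alone set answers a legitimate question. That stands as a reason to show the two groups separately, but not to leave one out. The analyses are also descriptive and the endpoints secondary, which limits the consequence.

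Several stronger readings are tempting, and the documents do not support them:

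- *Completeness can only be 100%.* Section 4.2 bases it on film or photographs plus the independent pathologist's assessment, and Section 8.2 does not say who judges complete resection for Per Protocol entry. The two can disagree. Section 5.7 also allows a second visit to finish a resection. Close to 100% is as far as the text goes.
- *Specimens are discarded.* Slides go back to the hospital for retention (Section 5.7.1) and data stay in the database (Section 5.3). The results are only left out of the summary.
- *A non-serious stenosis outside Per Protocol is recorded nowhere.* Section 6.0 records related adverse events of any seriousness, and Section 11.1 has the adjudicator review device- and procedure-related events. Section 6.2.1, however, restricts the adverse event form to related serious events, and Section 8.5 commits only to reporting adjudicated SAEs. A capture route exists on one reading and not on the other.
- *The 90-day return condition costs stenosis data.* Stenosis is assessed only at that endoscopy, so non-returners are missing under any set.

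Appendix 1 places the specimen review in the 90-day column, but that review needs the specimen, not the subject's return.

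**Conclusion.** The point holds. Following the plan as written, all four secondary endpoints are reported on a subset selected partly by procedural success, although the wider data are collected. On the central assumptions about a quarter of treated subjects (14.1/60 = 24%) are outside the set.

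A reader might take 46 of 60 as the plan's own result. It is one scenario, resting on 60 being treated subjects, on 0.85 being the device-alone share, and on independent loss at the anticipated maximum. The loss of precision is minor. The weight of the point lies in exclusion that depends on how the procedure went. Nothing in the documents shows that the excluded subjects do worse; the plan simply could not reveal it if they did.

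The conflict over non-serious related events between Sections 6.0 and 11.1 on one side and Section 6.2.1 on the other must be reconciled, because it decides whether the safety reporting can back up the stenosis endpoint.

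**What to change.** In Sections 8.4 and 8.6, replace the single assignment with a named set and a stated denominator for each endpoint:

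- stenosis: all treated subjects with a 90-day endoscopy;
- specimen diagnostic value: all subjects and lesions with a retrieved specimen;
- completeness: all treated lesions;
- persistence: all treated lesions with a 90-day endoscopy.

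Show each overall and by device-alone versus converted, with Per Protocol as a supportive view. Changing the population for the primary endpoint alone could leave the secondary assignment in place, so this needs its own edit. Reconcile Sections 6.0, 6.2.1 and 11.1 on which related events are recorded.

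The cost for the endpoints is SAP wording only, since the data are already collected. Reported rates may be slightly less favourable, and outcomes in converted subjects may partly reflect the other modality; the split display makes this visible.

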8.8 Sample Size

With a sample size of 60 and a success rate of 0.85, we can expect the 95% exact confidence interval to be between 0.782 and 0.967. Our goal is to achieve a confidence interval half width of our point estimate that is not greater than 0.10. The proposed sample size of 60 will provide a

confidence interval half width 0.0972, and so will meet the targeted precision for our point estimate. Further, because this study is a post-market, confirmatory, observational study, the sample size identified is consistent with post-market studies of similar devices.

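### Once one subject has two treated lesions, section 8.4 replaces the exact interval by a logistic GEE with no fallback, and that interval does not exist if no failure is observed

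*Combined protocol and SAP*

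**What the plan says.** Section 8.4 makes the interval method depend on lesion counts. If each subject has one lesion, "A confidence interval for the successful removal of all lesions will be calculated by Clopper-Pearson exact methods". If "one or more subjects are treated for multiple lesions, then a generalized estimating equation with a logistic link function will be used" to obtain the 95% interval of the success rate. The section names no cluster unit, working correlation, variance estimator or fallback for data without failures.

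The analysis set is Per Protocol. Section 8.2 limits it to subjects who "had complete lesion resection with the EndoRotor alone without any adjunctive modality resection", who had no eligibility deviation and who attended the 90-day visit. Technical Success (4.1 and 8.4) has two parts: resection without another modality, and no definite or probable device-related SAE through 90 days. Section 8.4 also says that the analysis concerns the share of lesions with persistent disease.

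Subjects with several lesions are foreseen. Inclusion criterion 2 in 4.3 sets a minimum of one lesion and no maximum, 5.7 tells sites to keep specimens from synchronous lesions apart, and 5.7.1 records how many lesions were treated. No number of such subjects is projected.

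**The concern.** One two-lesion subject is enough to discard a method that always returns an interval for one that returns none when every unit succeeds. The Per Protocol entry rule repeats the resection half of the endpoint, so it removes most routes to failure and pushes the observed rate towards 100%, which is where the logit breaks down. If that happens, the plan supplies no usable primary interval. The sponsor would then have to choose a method after seeing the data, or report an interval with no width.

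**Working it through.** **1. The plan's own figure.** Section 8.8 takes the exact method only and, for 60 subjects at 0.85, states that "we can expect the 95% exact confidence interval to be between 0.782 and 0.967". For 51/60 = 0.85, Clopper-Pearson has lower limit Beta(0.025; 51, 10) and upper limit Beta(0.975; 52, 9), giving 0.734 to 0.929 with half-width 0.0974. That agrees with the stated half-width of 0.0972, but the stated limits do not match: (0.967 − 0.782)/2 = 0.0925, and those limits belong to 45/50. This is a separate discrepancy and does not affect the present point.

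**2. What can still fail in the Per Protocol set.** Section 8.4 allows three readings of the quantity analysed.

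| Quantity | Failures possible in the Per Protocol set? | GEE interval |
|---|---|---|
| Removal of all lesions | No; fixed at 100% by 8.2 | Never exists |
| Technical Success | Only through a definite or probable device-related SAE | Lost if no such SAE occurs |
| Lesion persistence at 90 days | Yes; 8.2 does not restrict it | Nothing is forced |

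**3. The GEE with no failures.** For an intercept-only model with independence working correlation, the estimate solves Σ(y − p) = 0 with p = 1/(1 + e^(−b)). If every y = 1, then p = 1 and b is infinite. The robust standard error is √M / [N p(1 − p)], where N is the number of lesions and M is the sum of squared subject residual totals. Both M and N p(1 − p) are 0, so it is 0/0.

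Run in statsmodels with 60 subjects, 6 of them with two lesions (an assumed number), and all successes, the fit stopped at b = 26.57 with limits 26.30 to 26.83. On the probability scale that prints as 1.000 to 1.000. Other settings returned NaN. The exact per-subject lower limit for 60/60 is 0.025^(1/60) = 0.940, so the interval is 94.0% to 100%.

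**4. Chance of no failures under the Technical Success reading.** With SAE probability q per subject and 60 subjects it is (1 − q)^60. The documents give no device-related SAE rate, so q is assumed. Section 1.3.2 offers only general polypectomy ranges (bleeding 0–10.8%, perforation 0–2.3%).

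| Assumed q | 0.5% | 1% | 2% | 3% | 5% | 10% |
|---|---|---|---|---|---|---|
| (1 − q)^60 | 74% | 55% | 30% | 16% | 4.6% | 0.2% |

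**5. The GEE with at least one failure.** Take 60 subjects, one with two lesions (61 lesions), and one failure in a single-lesion subject.
- b = ln(60/1) = 4.094.
- M = [60² + 58 × 1² + 2²]/61² = 3662/3721 = 0.984.
- N p(1 − p) = 60/61 = 0.984.
- SE = √0.984/0.984 = 1.009, and 4.094 ± 1.96 × 1.009 gives 0.893 to 0.998.

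| Failures | GEE, independence, 61 lesions | Clopper-Pearson, 60 subjects |
|---|---|---|
| 1 | 0.893 to 0.998 | 0.911 to 0.9996 |
| 2 | 0.878 to 0.992 | 0.885 to 0.996 |
| 3 | 0.858 to 0.984 | 0.861 to 0.990 |
| 9 | 0.740 to 0.922 | 0.734 to 0.929 |

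**6. Coverage.** This was simulated with 60,000 runs per setting, subject-level failures, and 1, 5, 10 or 20 two-lesion subjects (assumed). When the GEE interval exists, it covers about 86% at q = 0.5%, 88–95% at 1% and 93–97% at 2–5%. If a missing interval counts as a miss, coverage is about 22%, 40–43%, 66–67% and 92% at q = 0.5%, 1%, 2% and 5%. Subject-level Clopper-Pearson covers 97% to 99.7% for q from 0.5% to 15%.

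**The case against.** The strongest defence is that the switch is pre-specified and triggered by lesion counts rather than outcomes, that a GEE is a standard way to handle clustered lesions, and that at the planned rate of 0.85 it works: failures are then practically certain and simulated coverage is about 95%. Section 8.0 calls the analysis primarily descriptive, and the plan has no hypothesis test or performance goal. The observed proportion is unaffected, and SAEs are adjudicated and reported separately. All of this stands. It lowers the severity but does not supply an interval when there are no failures.

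A reader might infer more than the documents support:
- **That the GEE also breaks down when nearly all lesions succeed.** It does not. One to three failures give finite intervals close to the exact ones, and coverage given an interval is clearly poor only at SAE rates of about 1% or less.
- **That the Per Protocol rule forces 100% success.** It fixes the resection component only. Subjects with device-related SAEs stay in the set and fail Technical Success, and persistence is not restricted.
- **That a missing interval is the most likely result.** This depends on an SAE rate that the documents do not give; at 5% the chance is only 4.6%.
- **That the switch abandons a subject-level estimand.** In the exact branch subject and lesion coincide, and afterwards an SAE can be coded to all of a subject's lesions. The plan should state the unit, but this is minor.
- **That planning precision only for the exact interval is an error.** It is ordinary practice when the number of extra lesions is unknown.

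**Conclusion.** The concern holds as a gap in the primary analysis, of moderate severity. Given at least one multi-lesion subject, the planned interval never exists if it is for removal of all lesions. If it is for Technical Success, it is missing with probability 55%, 30%, 16% or 4.6% at assumed SAE rates of 1%, 2%, 3% or 5%. These figures assume 60 Per Protocol subjects and independent events; a smaller set makes the chance larger. If lesion persistence is the variable analysed, the Per Protocol rule does not create the problem.

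The missing working correlation adds to the gap. In statsmodels an exchangeable structure returned NaN with exactly one two-lesion subject, at any number of failures. Other software may behave differently, but the plan does not say what to use.

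**What to change.** In section 8.4, define subject-level success: every treated lesion meets the resection criterion and the subject has no definite or probable device-related SAE through 90 days. Report its Clopper-Pearson interval whatever the number of lesions or, at minimum, whenever no failure is observed. Keep the GEE for the lesion-level rate as a supportive analysis, with subject as cluster, independence working correlation and robust variance, and only when at least one failure exists.

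The cost is about two sentences. The exact interval is somewhat conservative and gains nothing from extra lesions. The change does not cure the circular Per Protocol definition in 8.2: 60/60 with 94.0% to 100% would still say nothing about resection, because failures of resection are excluded beforehand. That needs its own correction.
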